## Addiction and Behavior Related to Menthol Cigarette Substitutes

### Abstract

Recent changes in population patterns of tobacco use in youth and adults underscore the potential substitution of other menthol tobacco products for cigarettes in the face of a ban on menthol in cigarettes. The increased use of cigars and pipe tobacco in youth following the 2009 ban on flavored cigarettes is particularly important given that flavored filtered little cigars are often indistinguishable from cigarettes and flavored pipe tobacco can be used to make roll-your-own cigarettes. Mentholated pipe tobacco (for roll-your-own cigarettes, mRYO), menthol filtered little cigars (mFLC), and non-menthol cigarettes (nmC) appear to be plausible substitutes for menthol cigarettes. The goal of the current study is to examine the abuse liability and substitutability of these potential menthol cigarette substitutes using an in-laboratory and *ad libitum* outpatient mixed design. One hundred current menthol cigarette smokers (n=50 aged 18-24 years, n=50 aged 25+ years) will complete a three-phase study: in Phase 1, utilizing a randomized crossover design, participants will complete 4 smoking sessions, smoking a different product each session to examine each product's abuse liability, demand, and topography. Products will include participants' usual brand menthol cigarette (UBMC) as well as 3 commercially-available alternatives, including mFLC, an mRYO product, and non-mentholated cigarette (nmC). Participants will complete one-week of daily diaries after smoking session 1 in phase 1 to assess their usage of usual brand menthol cigarette (UBMC). In Phase 2, to assess uptake, changes in subjective effects, and use over time, participants will select their preferred study product from Phase 1 and instructed to completely substitute the product for their UBMC for one week. Participants will complete daily diaries during this period to more accurately assess substitution and perceived effects in real-time. In Phase 3, participants will complete a final in-lab visit to assess the substitutability of their preferred product from Phases 1 and 2, under simulated ban conditions using a progressive ratio task. In all phases, multiple domains of abuse liability will be assessed, including product administration (in-lab topography and daily self-report measures), product liking/craving and withdrawal suppression (in-lab and daily diary self-report). This study will be the first to estimate the substitutability of potential menthol cigarettes substitutes in adult smokers, which could impact the health benefit of a public health standard banning menthol in cigarettes. It will evaluate characteristics and perceptions (e.g., satisfaction, taste) of these products that may increase the likelihood of substitutability. Findings from this study will provide key information on the potential unintended consequences of a ban on menthol in cigarettes (i.e., the extent to which these substitutes would appeal to and be used by existing menthol cigarette smokers). They may also inform how FDA treats other non-cigarette tobacco products used as menthol cigarette substitutes in future proposed rulemaking, for example, extending the ban to menthol filtered little cigars or menthol pipe tobacco.

#### Project Narrative/relevance to public health:

FDA has repeatedly indicated its intent to pursue a ban on menthol in cigarettes. However, estimating the impact of a potential ban on menthol in cigarettes requires accounting for likely substitutes in the marketplace that may also need to be restricted to effectively protect public health. The proposed study uses an in-laboratory and *ad libitum* outpatient mixed design to examine the abuse liability and substitutability of plausible menthol cigarette alternatives, including menthol filtered cigars, menthol roll-your-own cigarettes, and non-menthol cigarettes, in a sample of current adult menthol cigarette smokers.

### A. Specific Aims

While the prevalence of cigarette smoking in the U.S. has continued to decrease, the proportion of menthol cigarette users increased significantly from 35% in 2008-2010 to 39% in 2012-2014. [*Menthol cigarettes are*

## Addiction and Behavior Related to Menthol Cigarette Substitutes

associated with increased youth smoking initiation, increased nicotine dependence, and decreased adult cessation. Menthol smokers are also more likely to be of low socioeconomic status, female, black or Hispanic, and identify as LGBT compared to non-menthol smokers. **As these studies highlight, menthol is strongly associated with facilitating the initiation and maintenance of cigarette smoking, particularly among vulnerable populations.**

The 2009 Family Smoking Prevention and Tobacco Control Act banned characterizing flavors in cigarettes and their components. Tobacco companies, however, exploited loopholes in this regulation to maintain sales of their products. For example, Djarum, previously a clove flavored *cigarette*, launched clove filtered *cigars* in anticipation of the ban, and sales of their clove filtered cigars increased by more than 1400% between 2009 and 2012. Moreover, menthol was not included in the ban, and the use of menthol cigarettes as well as flavored cigars and pipe tobacco increased in youth following the flavored cigarette ban, suggesting substitution of other available flavored tobacco products. **Thus, while manufactured flavored cigarettes are no longer available, the public health benefit of this product standard was attenuated by the presence of accessible commercially-available substitutes in the marketplace.**

For any proposed regulatory action, the FDA must estimate the range of potential impacts on behavior and health. Estimating the impact of a potential ban on menthol in cigarettes, therefore, requires accounting for likely substitutes in the marketplace that may also need to be restricted to effectively protect public health. Current tobacco products, including [*menthol filtered little cigars (mFLC), menthol roll-your-own (mRYO) tobacco and cigarette tubes, and non-menthol cigarettes (nmC), are relevant targets.*

**The goal of the proposed study is to examine the abuse liability and substitutability of plausible menthol cigarette alternatives.** Using an in-laboratory and *ad libitum* outpatient mixed design, current menthol cigarette smokers (N=135) will complete a three phase, 3-week study: in Phase 1, utilizing a randomized crossover design, participants will complete [4 smoking sessions], smoking a different product each session to examine each product's abuse liability, demand, and topography. Products will include participants' usual brand menthol cigarette (UBMC) as well as 3 commercially-available alternatives, including mFLC, mRYO product, [*and non-mentholated cigarette (nmC).*] Participants will complete one-week of daily diaries after smoking session 1 in phase 1 to assess their usage of usual brand menthol cigarette (UBMC). In Phase 2, to assess uptake, changes in subjective effects, and use over time, participants will [*select their preferred study product from Phase 1*] and be instructed to completely substitute the product for their UBMC for one week. Participants will complete daily diaries during this period to more accurately assess substitution and perceived effects in real-time. In Phase 3, participants will complete a final in-lab visit to assess the substitutability of [*their preferred product from Phases 1 and 2,*] under simulated ban conditions using a progressive ratio task. In all phases, multiple domains of abuse liability will be assessed, including product administration (in-lab topography and daily diary self-report measures), product liking/craving and withdrawal suppression (in-lab and daily diary self-report).

**Aim 1: To assess the abuse liability of menthol cigarette alternatives.** *H1a: Alternatives will [have similar use topography and significantly reduce nicotine craving/withdrawal similar to UBMC, but (H1b) UBMC will show significantly greater demand indices and liking/satisfaction compared to alternatives. H1c: Among alternatives, nmC will show the greatest demand and liking/satisfaction, followed by mFLC, and lastly mRYO.]*

**Aim 2: To assess the substitutability of menthol cigarette alternatives.** [*H2a: A significantly higher portion of product preference selections for Phase 2 will favor nmC than all other alternatives. H2b: Participants' use of study products will significantly increase over the one-week substitution period. H2c: Under simulated UBMC ban conditions, >80% of participants will substitute at least 50% of their UBMC use with study product.]*

**Aim 3: To evaluate which product characteristics and perceived effects influence greater substitution.** *H3: Participants reporting higher product satisfaction, including "throat hit", menthol-specific sensory effects,*

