## Innovation

This study is poised to contribute to FDA's decision-making on menthol and to advance the field of tobacco regulatory science in a number of ways. It will be the first to estimate the substitutability of combusted menthol cigarette substitutes in adult smokers, which could attenuate the health benefit of a public health standard banning menthol in cigarettes. Previous studies have examined the addiction potential of cigarettes, including menthol cigarettes, but have not compared measures of abuse liability and substitutability across menthol cigarettes and likely menthol cigarette substitutes. This information is needed to determine how the availability of other menthol products may affect the public health impact of a ban on menthol in cigarettes [*and whether additional product standards would be needed (e.g., ban on menthol in filtered little cigars, pipe tobacco) to maximize the public health benefit of such a regulation.*] Second, this study pairs standardized measures of abuse liability, use patterns, and subjective effects in the lab with *ad libitum* outpatient use of the study product to approximate "real-world" use. Daily diaries will begin to elucidate real-time mechanisms associated with substitution. Finally, the high prevalence of menthol cigarette use in youth and young adults and recent data on the flavored cigarette ban suggest that a ban on menthol cigarettes may drive alternative product use in young smokers. [*Stratified sampling of young adults*

[figure not shown]

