**Figure 2. Study Overview**

in-person lab visits. At the beginning of each visit, pregnancy tests will be completed to ensure that the participant is not pregnant. During visit 1, participants will complete a PROP taste test to measure a participants' perceived intensity to taste. In *Phase 1*, utilizing a randomized crossover design, participants will complete [4 smoking sessions,] each session smoking a different product examining each [participants' puff topography while sampling the product, the product's ability to suppress nicotine craving/withdrawal, and the product's demand indices. Products will include participants' usual brand menthol cigarette (UBMC) as well as 3 commercially-available alternatives, including an mFLC, a pre-assembled mRYO product (menthol tobacco + menthol tube), and an nmC.] All sessions will occur following 12-hrs of nicotine abstinence and be separated by 48-hrs. Participants will complete daily diaries for one-week during this period to more accurately assess current use of their UBMC. In *Phase 2*, participants will [select their preferred study product from Phase 1] and be instructed to completely substitute the product for their UBMC for one week. Participants will complete daily diaries during this period to more accurately assess degree of substitution and perceived effects in real-time. In *Phase 3*, participants will complete a final in-lab visit to assess the substitutability of their preferred product, under simulated ban conditions using a progressive ratio task. In all phases, multiple domains of abuse liability will be assessed, including product administration (in-lab puff topography and daily diary self-report measures), product liking and craving and withdrawal suppression (in-lab and daily diary self-report), and hypothetical purchase tasks to simulate demand.

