### Recruitment Feasibility and Retention

**Recruitment:** We intend to recruit 135 current menthol cigarette smokers (and assume 20% attrition) over a 16-month period (4 months of study preparation, 16 months of recruitment, and 4 months of data cleaning/analysis and manuscript prep). Therefore, we need ~6 participants to be recruited and complete study procedures each month to achieve our goal; we are confident that our recruitment approaches will yield sufficient numbers given our successful history of recruitment for other tobacco-related research of similar design. Menthol cigarette smokers will be recruited from advertisements through a variety of media outlets and the internet, including Study Search, as well as community events. Participants from other studies who have agreed to be contacted regarding other study opportunities will also be contacted. Staff from those studies will prepare contact letters/emails and call participants on behalf of this study. Participants interested will be referred to this study for screening. Participants will access the screening questionnaire using a public survey link generated by REDCap. Based on our team's previous studies we conservatively assume a 20% attrition rate; thus, we will need to recruit 135 participants to have 80 complete the study. Menthol smokers will be screened over the telephone. Participants who meet the following eligibility criteria will be asked to take part in the study.

**Inclusion Criteria:** 1) a current menthol cigarette smoker (>90% menthol cigarette use;  $\geq 5$  cigarettes per day) for at least the past 6 months, 2) between 21-24 (young adult or 25-50 years old (aged 25+), 3) willing to provide informed consent and abstain from all tobacco and nicotine use for at least 12 hours prior to the five lab sessions, 4) willing to complete two weeks of daily dairies, 5) read and speak English, and 6) have access to a smart phone or email

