Modified Cigarette Evaluation Questionnaire (mCEQ)	X	X	X	X	X
Tiffany-Drobes Questionnaire of Smoking Urges: Brief Form (modified)	X	X	X	X	X
MNWS	X	X	X	X	X
Cigarette Purchase Task	X	X	X	X	X
Subjective effects (Daily Diary)	X			X	
Substitutability					
Cross Price Elasticity Task		X	X	X	X
Progressive ratio task (UBMC vs. study product - computer task)					X
Record final product selected				X	
Use behavior (Daily Diary)	X			X	
Daily diary					
· # Study products smoked				X	
· # Non-study products smoked	X			X	
· Other tobacco use	X			X	
Modified Cigarette Evaluation Questionnaire (mCEQ)	X			X	
Drug Effects/Liking Questionnaire	X			X	
Behavioral Intentions				X	
Tiffany-Drobes Questionnaire of Smoking Urges: Brief Form (modified)	X			X	
MNWS	X			X	

Addiction and Behavior Related to Menthol Cigarette Substitutes

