### 2. Data Analytic Plan

Statistical analyses will be performed using SAS 9.4 and an alpha of .05. Background measures will be summarized by product (UBMC, mFLC, mRYO, nmC), as appropriate. Continuous variables will be presented as mean  $\pm$  SD; categorical variables will be presented as counts and proportions. We will apply a transformation to normalize the distribution and stabilize the variance of the residuals where appropriate.

Hypotheses 1a and 1c: We will use Repeated Measures Analysis of Variance with Tukey-adjustment to examine differences between the alternatives and the UBMC in abuse liability assessed at each product lab session. Assuming statistically significant product differences, this post-hoc test will allow us to not only compare each product to the UBMC, but will also allow comparison of the alternative products with each other. Because product introduction in Phase 1 will be randomized using a Latin Square, a fixed effect for session and a random effect for sequence will be included in all analyses.

Hypothesis 2a: Product preference will be examined using a Chi-Square Test, comparing the proportions of participants choosing each alternate product for further use.

Hypothesis 2b: We will examine the trajectory of use behavior outcomes using Linear Mixed Model (LMM) regression analysis. We will employ a random intercept or slope parameter, as appropriate, and model the covariance structure for the repeated outcome measures, while accounting for potential confounders, including gender and baseline cigarettes/day.

Hypothesis 2c: This aim will be analyzed as a Chi-Square Test of Goodness of Fit to test the proportion of use compared to 80%.

Hypothesis 3: We will examine whether differences in product characteristics and changes in perceived effects collected via daily diary are associated with increased substitution of the alternate product over the seven-day period using generalized LMM regression analysis, similar to that outlined in H2b.

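### A significant H2a chi-square on first choices would not by itself show that menthol smokers prefer the non-menthol cigarette to menthol substitutes; contrasts and a combined menthol share should be prespecified

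*Combined protocol and SAP*

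**What the plan says.** Section A (Specific Aims, Aim 2) states H2a: "A significantly higher portion of product preference selections for Phase 2 will favor nmC than all other alternatives". The choice set, described in D.1 (Design Overview), is "3 commercially-available alternatives, including an mFLC, a pre-assembled mRYO product (menthol tobacco + menthol tube), and an nmC", so two of the three options carry menthol and one does not.

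In Table 1 (D.3 Measures) the choice itself is captured by one line at Visit 4, "Record final product selected". No ranking or second choice is listed.

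E.2 (Data Analytic Plan) gives the whole H2a analysis in one sentence: "Product preference will be examined using a Chi-Square Test, comparing the proportions of participants choosing each alternate product for further use". The general rule is "Statistical analyses will be performed using SAS 9.4 and an alpha of .05". For H2a the plan states no pairwise contrast, no comparison of the menthol products combined with nmC, and no confidence interval. The power section (E.1) covers H1a and H2c, not H2a.

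On use of the results, the Innovation section says the information is needed to judge "whether additional product standards would be needed (e.g., ban on menthol in filtered little cigars, pipe tobacco"). The Implications paragraph of Section B makes the same point about extending a ban to these two menthol products.

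**The concern.** Anyone who wants a menthol substitute has two places to go, while anyone content with non-menthol has one. First-choice counts therefore divide menthol preference across two cells. An omnibus chi-square adds a second problem: it can be significant because mRYO is unpopular, whatever the relation between nmC and mFLC.

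At stake is the interpretation. A report that nmC was significantly preferred could be taken to mean that non-menthol cigarettes are the main substitute and the menthol alternatives matter less. The same data may be compatible with about half of participants choosing menthol, or with nmC and mFLC being indistinguishable. That difference bears on the regulatory question the study is meant to inform.

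**Working it through.** **Inputs.** Alpha is 0.05 (E.2). The number analysed is 80 completers, from "we will need to recruit 135 participants to have 80 complete the study" (Recruitment Feasibility and Retention). The equal-shares null (1/3 each) is an assumption, because the plan does not state one. The plan gives no H2a effect size, power or sample size to reproduce. The splits below are illustrations, in the order nmC/mFLC/mRYO.

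**Omnibus test.** The statistic is the sum of (observed − 80/3)² / (80/3), on 2 df, with 80/3 = 26.67.

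- 35/32/13: (8.33² + 5.33² + 13.67²) / 26.67 = 10.675, p = 0.005.
- 38/21/21: (11.33² + 5.67² + 5.67²) / 26.67 = 7.225, p = 0.027.

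Both are significant with nmC the largest cell.

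**Pairwise contrasts and combined share.** These use exact two-sided binomial tests against one half.

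| Split | nmC vs mFLC | nmC vs mRYO | Chose menthol | nmC share vs 50% |
|---|---|---|---|---|
| 35/32/13 | p = 0.81 | p = 0.002 | 45/80 (56%) | p = 0.31 |
| 38/21/21 | p = 0.036 | p = 0.036 | 42/80 (52.5%) | p = 0.74 |

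The exact 95% CI for 42/80 is 41% to 64%. In the first split the omnibus result is driven by mRYO. In the second, nmC leads each rival, but the data do not favour non-menthol over menthol in either direction. For nmC to exceed 50% significantly, at least 50 of 80 would have to choose it (62.5%).

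**How often this could arise.** In a multinomial simulation with an assumed true split of 46/27/27% and n = 80, the omnibus test is significant with nmC largest in 57% of trials. The test of nmC against the two menthol products combined favours nmC in 0.2%.

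**How wide the window is.** At n = 80, with nmC below half and both pairwise tests required at 0.05, only 38 or 39 nmC choices qualify. With both required at a Bonferroni level of 0.025, none do.

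The sample size is itself unclear. The plan says "we conservatively assume a 20% attrition rate", but 135 × 0.80 = 108, and 80 / 0.80 = 100, not 135. At 108, the split 52/28/28 gives omnibus p = 0.005 and pairwise p = 0.0097 each, which passes 0.025, with 56/108 (52%) choosing menthol.

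**Head-to-head, nmC against mFLC.** This needs the second choices of those who chose mRYO. Taking first choice to mean preferred, mFLC needs 41 of 80:

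- 35/32/13: 41 − 32 = 9 of the 13 mRYO choosers.
- 38/21/21: 41 − 21 = 20 of the 21. If half of them preferred mFLC, nmC would win by about 49 to 31.

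The recorded selection cannot tell these cases apart.

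**The case against.** The strongest reply is that H2a claims only product shares. It predicts that more selections will go to nmC, and 38/21/21 would bear that out. Nothing in the documents says H2a will demonstrate preference for non-menthol over menthol. This stands: the hypothesis is not wrong as written. What needs guarding is the conclusion drawn from it.

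Second, every participant is to try all three alternatives. H1c predicts an order among them on demand and liking, and the Tukey comparisons in E.2 set the alternatives against one another. So the plan already holds within-person evidence on nmC against mFLC. This stands in part. The evidence is indirect, is not linked to H2a, and concerns mean ratings and demand rather than choice. The cross-price task pairs each product with the usual brand, not nmC with mFLC.

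Third, if the wording of H2a meant the other alternatives combined, 38/21/21 would fail it (38 against 42) and the vote-splitting problem would vanish. That is possible, but the analysis sentence compares the share of each product.

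A reader might go further and infer that most participants would really take mFLC over nmC, or that menthol is the majority preference. The documents support neither. At 38/21/21 the reversal needs 20 of 21 mRYO choosers to move one way, and the interval for the menthol share spans one half. Nor is estimating shares after removal of a further product a stated aim, so its absence is not a failure to deliver.

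**Conclusion.** The point holds as a limit on interpretation. With the planned omnibus test at n = 80, nmC can be significantly largest while not beating mFLC (35/32/13: p = 0.005 overall, p = 0.81 head to head among first choices). It can also beat each rival while about half choose menthol (38/21/21: 52.5%, 95% CI 41% to 64%). A significant H2a therefore does not by itself show preference for non-menthol over menthol substitutes.

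This rests on an equal-shares null, on one chi-square being the whole H2a analysis, and on the chosen splits being possible rather than expected. Where both pairwise tests must succeed, the n = 80 window is narrow. Whether mFLC would win a direct contest with nmC is unknown, because second choices are not recorded. The trial remains valid, and the remedy is cheap.

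**What to change.** In E.2 under H2a:

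1. State the null for the omnibus test, and prespecify nmC against mFLC and nmC against mRYO with multiplicity control. Say whether H2a requires both to succeed.
2. Report the combined menthol (mFLC + mRYO) against nmC first-choice share with a 95% CI.
3. Limit the H2a conclusion to what these results show, and say that a plurality for nmC is not evidence of preference for non-menthol over menthol.

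Items 1 to 3 need no new data.

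In Table 1, add one second-choice item at Visit 4, next to the final selection. Head-to-head preference can then be estimated in all participants. In the 38/21/21 example, first choices alone inform nmC against mFLC in only 38 + 21 = 59 of 80. Treat redistributed shares after removing a product as exploratory.

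The cost is one more question at a visit already held, a few more prespecified comparisons, and the stricter threshold that multiplicity control brings.

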## Addiction and Behavior Related to Menthol Cigarette Substitutes

*craving reduction, improved mood with use, and ease of use [on daily diaries, will report the greatest substitution of study product for UBMC.]*

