## Addiction and Behavior Related to Menthol Cigarette Substitutes

12 hours of overnight tobacco abstinence, biochemically verified by exhaled carbon monoxide ( $eCO \leq 10\text{ppm}$ ). Sessions will be separated by a standard 48-hour washout period. Participants will smoke one cigarette ad libitum and a puff topography device will discretely record smoking behavior throughout the session, including puff duration, number of puffs, puff volume, and time between puffs.  $eCO$ , and self-report measures of craving and withdrawal will be recorded immediately before and at several times after the smoking session. Self-report measures of abuse liability will also be completed during the sessions. During the preferred study product observational use period, participants will be provided a weeks' worth of a potential menthol substitute at no cost. Consistent with our previous switching studies, study products will be provided in a 1.2 to 1 ratio based on self-reported use at the time of screening. This slight over appropriation helps to ensure that participants have enough study product available so to not artificially limit use, while also not oversupplying and potentially artificially increasing use behind what would be usual. Participants will be instructed to completely switch and exclusively use the study product during the 1-week time period. During this period, participants will complete daily diary once a day. Following the one-week use period, participants will come to the lab following 12-hr nicotine abstinence confirmed by  $eCO$ . To simulate the effect that restricting menthol in cigarettes would have on increasing (or not) preference for other alternative menthol substitutes, participants will complete a 90-minute concurrent choice task with differential cost (effort) required to earn 2 puffs from their UBMC (10 clicks increasing to 7200) versus their preferred study product (always 10 clicks) from Phase 2. . This session will last approximately 3 hours.

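### Aim 3 asks what influences substitution, but its only planned test relates use to ratings from the same once-daily diary with no time ordering, so effects of use can be reported as drivers

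*Combined protocol and SAP*

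**What the plan says.** **The question.** Section A states Aim 3 as "To evaluate which product characteristics and perceived effects influence greater substitution". The Innovation section adds "Daily diaries will begin to elucidate real-time mechanisms associated with substitution", and the Abstract says that the findings may inform FDA rulemaking.

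**The hypothesis.** H3 takes both sides of the comparison from one instrument. Participants who rate satisfaction, craving reduction, mood with use and ease of use more highly "on daily diaries, will report the greatest substitution of study product for UBMC".

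**The instrument.** Under D.2, in the substitution week, "participants will complete daily diary once a day". Table 1 (D.3) places the counts of study and non-study products in that diary, beside the mCEQ, Drug Effects/Liking, urge and withdrawal scales.

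**The analysis.** E.2 asks whether product characteristics and "changes in perceived effects collected via daily diary are associated with increased substitution of the alternate product over the seven-day period", using a generalized linear mixed model like the one for H2b. The H2b model is fitted "while accounting for potential confounders, including gender and baseline cigarettes/day". For H3 the plan mentions no lag, no prior-day use and no rating taken before Phase 2. It does not say whether rating and use are paired on the same day.

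**The concern.** The aim asks about direction, and the planned test carries no information about direction. Some H3 predictors, such as craving reduction and improved mood with use, are by their own wording effects of using the product. A participant who smokes more of it on a given day may for that reason report more of them. The regression would show the same positive coefficient whether perception drives use or use produces perception.

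If so, H3 could be declared supported although perceptions have no effect on substitution. Under an aim worded in terms of influence, the features offered to a regulator as drivers could then be consequences of use. Splitting the coefficient into within- and between-person parts does not help, because the reverse path operates within the day.

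**Working it through.** The plan gives no effect size, power or sample size for H3 (E.1 powers H1a and H2c only), so there is no stated figure to reproduce. The check is of time order, with a simulation to show its consequence.

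**Inputs from the documents:** 80 completers (D.2, Recruitment); 7 diary days and alpha .05 (E.2); one diary a day (D.2).

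**Assumed, because the documents give no figure:** the reverse effect b (change in the same-day rating per unit of use), the variances, and the day-to-day autocorrelation.

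**Simulated truth.** Use y(it) = u(i) + e(it). Rating x(it) = b·y(it) + v(i) + noise. The rating has no effect on use. All SDs are 0.7 and the autocorrelation of e is 0.3.

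**Hand check.** With equal variances and no autocorrelation, the slope of y on same-day x is b/(1 + b²), although the true effect is 0:
- b = 0.1: 0.1/1.01 = 0.099
- b = 0.3: 0.3/1.09 = 0.275
- b = 0.5: 0.5/1.25 = 0.400

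The simulated mean coefficients, with autocorrelation, were 0.096, 0.249 and 0.373.

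**False findings** (share of 100 simulated trials with p < .05; Monte Carlo margin at 5% is 1.96 × √(0.05 × 0.95/100) = 4.3 points):

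| b | same-day diary model | previous-day rating, adjusted for previous-day use | Phase 1 lab rating |
|---|---|---|---|
| 0 | 4% | 3% | 9% |
| 0.1 | 69% | 4% | 0% |
| 0.3 | 100% | 9% | 3% |
| 0.5 | 100% | 5% | 7% |

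Runs of 1,000 trials, with random-intercept SD equal to the daily SD and autocorrelation 0 or 0.3, gave for the same-day model 5.2% at b = 0, 63% to 65% at 0.1, and at least 99.8% at 0.2 and 0.3. The lagged model gave 3.7% to 5.8% and the Phase 1 rating 4.4% to 5.7%. A further run gave 72% at 0.1 and 100% at 0.2 for the same-day model, against 5% to 7% for the lagged one.

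**What the time-ordered models cost** (same n and days; effects again assumed):
- *True same-day effect of rating on use, slope 0.2.* Detected in 98% to 99.5% of trials by the same-day model, 8% to 12% by the lagged model and 19% to 25% by the Phase 1 rating.
- *Only day-to-day variation in the rating matters.* The lagged and Phase 1 models detect 5% to 6%, no better than chance.
- *A stable trait raises both rating and use, with no causal effect.* With loading 0.6, the Phase 1 rating is falsely significant in 40% to 41% and the same-day model in 10% to 13%. Another run gave 33% and 15%.
- *Ratings respond to cumulative use (0.3), with no effect on use.* The lagged model rejects in 8% to 12%.

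**Outcome days.** 80 × 7 = 560 diary days fall to 80 × 6 = 480 with a one-day lag, a loss of 1/7, or 14%.

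**The case against.** The strongest reply is that E.2 promises only an association, that H3 itself is worded as one, and that the Innovation section speaks of beginning to elucidate. This stands against the inference that consequences of use will be reported as drivers: the plan does not say so, and only *can* is supported. It does not dispose of the point, because this model is the only test of an aim that asks what influences substitution.

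Second, timing is partly inferred. The documents give neither the hour of the diary nor its recall window, so they do not establish that ratings follow the day's use. Same-day pairing is the natural reading of a once-daily diary with no lag stated, but it is not explicit. The reference to changes in perceived effects does not settle it: no reference point is defined, and a change can also follow use.

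Third, an effect produced by smoking can still drive later smoking, so being a consequence does not exclude being a driver. H3 also covers product characteristics, to which reverse causation applies less clearly. Both remarks are fair. They show that the same-day coefficient is ambiguous, not that it is wrong.

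Fourth, the simulation assumes the reverse effect that it then detects. It also uses a Gaussian outcome, where the plan has a ratio of study product to usual brand and a generalized model. That stands: the rejection rates are illustrations.

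Finally, a reader might infer that the Phase 1 lab rating should replace the diary rating as the H3 predictor. The documents do not support that. H3 specifies diary perceptions, the lab rating rests on one smoked product, and in the runs above it lost most of the power and did worse than the same-day model under a shared trait. Nor does any text show that days without study-product use would drop out of the model.

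**Conclusion.** The point holds in a limited form. Aim 3 asks about influence, and its only planned analysis has no time ordering, so perceptions produced by use can be presented as drivers. With an assumed reverse effect of 0.1 and no true effect of perception, the same-day model was significant in 63% to 72% of simulated trials, and in nearly all at 0.2 or more. The time-ordered models stayed near 5% in the same settings. The size rests on the assumed effect, variances and Gaussian outcome. The inability to tell direction does not, provided that reports are paired on the same day.

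A reader might take the 63% to 72% as the trial's false-positive rate for H3. The documents give no figure for the reverse effect and so do not support that. This is a correction worth making to a hypothesis that is not powered; it does not make the diary analysis invalid as a description.

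**What to change.** In E.2, Hypothesis 3:

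1. Keep the planned diary model. State that ratings and substitution are paired on the same day, limit the conclusion to association, and reword Aim 3 to match.
2. Prespecify an added analysis of day t substitution on the day t−1 rating, adjusted for day t−1 substitution. Prespecify also a supporting analysis of Phase 2 substitution on the chosen product's rating at its own Phase 1 lab session.
3. Claim direction only where these two time-ordered analyses agree, and say that confounding by stable traits remains even then.

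**Cost.** No new data are needed: Table 1 already lists the mCEQ, Drug Effects/Liking, urge and withdrawal scales at the lab visits as well as in the diary. Where an H3 item was asked only in the diary, only the lagged analysis applies. The lagged analysis loses day 1 as an outcome (480 of 560 diary days remain). Both added analyses have low power for same-day effects, so the plan should state that a null result there does not show that perceptions have no influence.
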